4.2. Scientific Rationale for Study Design

The study will utilize Simon two-stage optimal design for targeted therapy (Simon, 1989). This design allows determination of AL101 anti-tumor activity while minimizing the expected sample size. The study will also include a lead-in cohort to establish the safety of AL101 administered at 6 mg QW with the described pre-medication as described in Section 6.6 and safety management as detailed in Section 6.4.

The primary endpoint, proportion of subjects with an ORR (CR+PR), was selected based on the FDA guidance from December 2018 on endpoints in oncology studies (FDA, 2018).

4.2.1. Rationale for Study Population

The primary target population for this study is subjects with recurrent or metastatic TNBC. This population is selected based on the mechanism of action of AL101, nonclinical and preliminary clinical data with AL101, as well as the pathophysiology of TNBC. Based on preliminary nonclinical and clinical emerging data, Notch-activated TNBC patient populations are selected to receive AL101 as monotherapy.

In TNBC patient-derived xenograft (PDX) tumor models, the presence of an activated Notch pathway signature and Notch mutations/fusions correlates with a significant response to AL101 monotherapy ([Broner, 2019](#)). Therefore, the Sponsor will test the hypothesis that subjects diagnosed with TNBC bearing Notch-activated gene alterations responds to AL101 monotherapy.

Importantly for the purposes of this study, the definition of TNBC has been evolving over the past few years. According to the 2010 guidelines by the American Society of Clinical Oncology (ASCO) and the College of American Pathologists (CAP), to qualify for TNBC, estrogen receptor (ER)/progesterone receptor positivity was defined as $\leq 1\%$ positively stained cells by IHC ([Hammond, 2010](#)). However, several studies show that tumors with $1\% < ER < 10\%$ behave similarly to those with $ER \leq 1\%$ ([Deyarmin, 2013](#); [Prabhu, 2014](#); [Yi, 2014](#)). Therefore, Fujii et al. recommends to define TNBC as human epidermal growth factor receptor 2 (HER2) negative BC with ER and/or progesterone receptor less than 10% ([Fujii, 2016](#)). Thus, subjects with less than 10% IHC staining of ER/progesterone receptor will be eligible to participate.

4.3. Justification for Dose

The dose selected for this study (6 mg QW) is based on nonclinical studies, prior clinical studies conducted by BMS (the previous developer) (CA216001, CA216002 and CA216003) and preliminary outcome from the ongoing ACCURACY study conducted by Ayala (NCT03691207). Please also refer to the Investigator's Brochure for further information.

Study CA216001 was a first in human dose escalation study which evaluated doses ranging from 0.4 mg QW to 8.4 mg QW. In the initial dose-escalation, there were no dose limiting toxicities (DLTs) noted in 4 subjects at 6 mg QW. Dose escalation was continued to 8.4 mg QW and DLTs, including a Grade 5 liver failure in one subject, were noted. The case of liver failure was complicated by pre-existing liver injury and possible contribution of an investigational nucleoside analogue, the subject had previously received, known to cause delayed liver toxicity. Consequently, an additional 10 subjects were enrolled at the 6 mg QW dose. There were 4 DLTs observed amongst 4 of these additional subjects including 2 subjects with Grade 3 diarrhea, 1 subject with Grade 3 vomiting/Grade 3 lipase elevation, and 1 subject with Grade 3 large intestinal ulcer with a non-treatment related Grade 3 infectious colitis. Based on this data, the previous sponsor assessed the RP2D as 4 mg QW.

However, upon careful review of these data, Ayala concluded that, with proper control of diarrhea, 2 of the DLTs which were noted at 6 mg QW could probably have been controlled so that they were potentially not DLTs. Importantly this is further substantiated by the observation in the ongoing ACCURACY study that (AL-ACC-01), with proactive control of diarrhea, there was only a 3% (2/34) incidence of Grade 3 diarrhea as opposed to the 19% (8/43) incidence noted in CA216001. The proactive control of diarrhea is delineated below and includes frequent and early use of loperamide followed by a low threshold to use steroids.

Furthermore, study CA216002 evaluated subjects with T-ALL/T-LL at the 6 mg QW dose. The subjects in this study tolerated the 6 mg QW dose well with no reported DLTs.

From a mechanistic perspective interest in using the higher dose of AL101 is driven by PK and pharmacodynamic (PD) results from the Phase 1 Study CA216001 indicate that AL101 exposure (C_{max} and area under the curve [AUC]) increases with approximately linear kinetics for QW

dosing across all doses tested. Furthermore, PD results (Hes1 expression in peripheral whole blood) from Study CA216001 indicate greater maximum effect and duration of target inhibition when increasing the QW dose from 2.4 mg to 4 mg to 6 mg and appears to reach a plateau at 8.4 mg QW. Most notably, the 6 mg dose achieved a considerably larger reduction in Hes1 and Hes4 than the 4 mg dose. This observation further supports using the 6mg QW dose.

Hence, the data from the 3 studies mentioned above (CA216001, CA216002 and ACCURACY) indicate that the 6 mg QW dose appears to be tolerated, especially if one implements proactive steps to manage the diarrhea. In addition, the PD data strongly suggests that the PD markers, Hes1 and Hes4, will be decreased to a much larger extent at 6 mg than at 4 mg, indicating better inhibition of Notch. In this new trial, safety will be closely monitored with specific instructions on how to control diarrhea, dose modification guidelines, and close monitoring of the subjects.

In the Phase 2 ACCURACY study, preliminary results have been reported. As of October 11, 2019, the safety analysis set included 29 subjects with adenoid cystic carcinoma. The most frequently reported AEs (>30% of all treated subjects), regardless of causality, were nausea, fatigue, diarrhea and vomiting. SAEs were reported for 14 subjects (48.3%) with pneumonia reported by 3 subjects (10.3%), all other events were single incidences. Treatment-related SAEs included infusion site reactions (2 reactions in one subject) and keratoacanthoma (each, 1 subject, 3.4%). The ACCURACY study is ongoing and expanded to include AL101 6 mg QW dosing schedule.

The observed safety profile of AL101 in the ACCURACY study to date suggests a lower rate of TEAEs of Grade 3 and above than previously reported for AL101 Phase 1 studies conducted by the previous developer. Notably, using the toxicity management guidelines for gastrointestinal (GI) adverse events in this protocol (outline in Section 6.4), the rate of Grade 3 diarrhea was reduced to 3.4% vs. 19.1% in the ongoing ACCURACY study vs. study CA216001, respectively. This suggests that with a rigorous control of GI toxicity, a dose of 6 mg is safe to administer to subjects with advanced cancer.

4.4. Study Duration

For each subject, the study is expected to last as follows:

Screening period:	Up to 28 days
Treatment period:	Until disease progression, unacceptable toxicity, or consent withdrawal
EOS:	30 days after the last administration of IP
Long term follow-up:	Every 3 months for the first year after EOS, then every 6 months for the next 2 years and then annually

4.5. End of Study Definition

A subject is considered to have completed the study if he/she has completed EOS visit.

The end of the study is defined as the date of the last visit of the last subject in the study.

5. ELIGIBILITY CRITERIA

Prospective approval of protocol deviations to recruitment and enrollment criteria, also known as protocol waivers or exemptions, is not permitted.

5.1. Inclusion Criteria

To be eligible for participation in this study, subjects must meet all the following criteria:

Age

1. At least 18 years of age (inclusive) at the time of signing the Informed Consent Form (ICF).

Type of Subject and Disease Characteristics

2. Have at least one measurable lesion per RECIST v1.1.
3. Have formalin-fixed paraffin-embedded (FFPE) tissue available from a metastatic lesion; a tumor block or 25 unstained slides from an archived (within 2 years) or fresh tumor samples (core or punch needle biopsy) are acceptable.
4. Documented tumor progression following no more than 3 lines of systemic chemotherapy, PARP inhibitor therapy or immunotherapy for metastatic disease, as appropriate. Of note, neoadjuvant and adjuvant therapy will not count as prior lines of therapy.
5. Histologically confirmed diagnosis of inoperable locally advanced or metastatic TNBC defined as ER and progesterone receptor staining <10%, and HER2-negative defined as IHC 0 to 1+
Note, if IHC is equivocal then do fluorescence in situ hybridization (FISH) or in situ hybridization (ISH); negative will be acceptable.
Note: if FISH or ISH is equivocal then further assessment is allowed with Sponsor written approval.
6. Documented Notch activation from tumor biopsy results from within the last 2 years from a commercially available NGS assay, LDT or other validated IUO clinical trial assay.

Gender and Reproductive Considerations

7. Female or Male subjects.
8. Women of childbearing potential (WOCBP) must have a negative serum or urine pregnancy test (minimum sensitivity 25 IU/L or equivalent units of HCG) within 24 hours prior to the start of IP and must agree to have a pregnancy test at least every cycle (4 weeks). An extension up to 72 hours is permissible in situations where results cannot be obtained within the standard 24-hour window.

Contraception use by men or women should be consistent with local regulations regarding the methods of contraception for those participating in clinical studies.

9. WOCBP must agree to use a highly effective birth control during the study (prior to the first dose with AL101 and for 120 days after the last dose), if conception is possible during this interval. Female subjects are considered to not be of childbearing potential if they have a history of hysterectomy or are post-menopausal defined as no menses for 12 months without an alternative medical cause.
10. Male subjects with partners who are WOCBP should use a combination of the methods specified in Section 10.4 for the women along with a male condom during the study and for 120 days after the last dose of IP, unless permanently sterile by bilateral orchidectomy.

Informed Consent

11. Capable of giving signed informed consent form (ICF) which includes compliance with the requirements and restrictions listed in the ICF and in this protocol.

5.2. Exclusion Criteria

The subjects must be excluded from participating in the study if they meet any of the following criteria:

Medical Conditions

1. A known additional malignancy that is progressing or requires active treatment that is considered medically active and may interfere in the ability to detect responses in this subject. Exceptions include basal cell carcinoma of the skin, squamous cell carcinoma of the skin that have undergone potentially curative therapy or in situ cervical cancer. Any exceptions should be discussed with the Sponsor's Medical Monitor.
2. BC that, in the opinion of the investigator, is considered amenable to potentially curative treatment.
3. Symptomatic central nervous system (CNS) metastases. Subjects with asymptomatic CNS metastases as well as those with previously treated CNS metastases are eligible for enrollment in the study if at least 28 days has elapsed since definitive treatment (either surgery, whole brain radiotherapy, stereotactic radiation), steroid therapy is either not required or dose has been weaned off over last 14 days, and the subject is deemed clinically stable by the investigator.
4. Current or recent (within 2 months of IP administration) gastrointestinal (GI) disease or disorders that increase the risk of diarrhea, such as inflammatory bowel disease and Crohn's disease. Non-chronic conditions (e.g., infectious diarrhea) that are completely resolved for at least 2 weeks prior to starting IP are not exclusionary.
5. Developed immune-mediated colitis with immunotherapy unless resolved to G1 or lower and without requirement of steroid treatment for at least 14 days prior to first dose of IP.
6. Peripheral neuropathy \geq Grade 2 for at least 14 days prior to first dose of IP.

7. Evidence of uncontrolled, active infection, requiring systemic anti-bacterial, anti-viral or anti-fungal therapy \leq 7 days prior to administration of IP such as known active infection with hepatitis B, hepatitis C, or human immunodeficiency virus (HIV).
8. Unstable or severe uncontrolled medical condition (e.g., unstable cardiac or pulmonary function or uncontrolled diabetes) or any important medical illness or abnormal laboratory finding that would, in the investigator's judgment, increase the risk to the subject associated with his or her participation in the study.
9. Pregnant or breastfeeding or expecting to conceive children within the projected duration of the study.

Diagnostic Assessments

10. Eastern Cooperative Oncology Group (ECOG) performance status \geq 2.
11. Abnormal organ and marrow function defined as:
 - a. neutrophils $<1000/\text{mm}^3$,
 - b. platelet count $<75,000/\text{mm}^3$,
 - c. hemoglobin $<8 \text{ g/dL}$,
 - d. total bilirubin $>1.5 \text{ times upper limit of normal (ULN)}$ (except known Gilbert's syndrome whereby the total bilirubin must be $\leq 5 \text{ mg/dL}$),
 - e. aspartate aminotransferase (AST) and alanine aminotransferase (ALT) $>2.5 \text{ times ULN}$ OR $>5 \text{ times ULN}$ for subjects with liver metastases,
 - f. serum creatinine $> \text{ULN}$ and creatinine clearance (CrCl) $<50 \text{ mL/min}$ (calculation of CrCl will be based on acceptable institution standard),
 - g. uncontrolled triglyceride \geq Grade 2 elevations per CTCAE v5.0 ($>300 \text{ mg/dL}$ or $>3.42 \text{ mmol/L}$).
12. Myocardial infarction within 6 months prior to enrollment or has New York Heart Association (NYHA) Class III or IV heart failure, uncontrolled angina, severe uncontrolled ventricular arrhythmias, or electrocardiographic evidence of acute ischemia or active conduction system abnormalities.
13. Mean QT interval corrected for heart rate using Fridericia's formula (QTcF) \geq 480 msec.

Prior/Concurrent Therapy

14. Completed palliative radiation therapy < 7 days prior to initiating IP.
15. Prior treatment with gamma secretase inhibitors. Prior treatment with anti-Notch antibodies may be allowed upon discussion with the Sponsor's medical monitor.
16. Last chemotherapy, biologic, or investigational therapy agent at least 4 weeks or 5 half-lives (whichever is shorter) prior to initiating IP; at least 6 weeks if the last regimen included BCNU or mitomycin C. Prior treatment with investigational monoclonal antibody will be reviewed case-by-case by the Sponsor.
17. Receiving chronic systemic steroid therapy (in dosing exceeding 10 mg/day of prednisone or equivalent) or any other form of immunosuppressive therapy within 7 days

prior to the first dose of IP. The use of physiologic doses of corticosteroids may be approved after consultation with the Sponsor.

18. Use of strong inhibitors of CYP3A4 within 1 week or 5 half-lives (whichever is longer) or strong inducers of CYP3A4 within 2 weeks or 5 half-lives (whichever is longer). Refer to Section 10.5.

Other Exclusions

19. Concurrent enrolment in another clinical study, unless it is an observational (non-interventional) clinical study or during the follow-up period of an interventional study.
20. Life expectancy of less than 3 months.
21. Hypersensitivity to AL101 and any of its excipients.

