6.4.4. Guidelines for the Management of Colitis

For management of colitis see [Table 4](#).

Table 4 Colitis Management

Grade	Dose Modification	Management
Any Grade		
 Subjects should be thoroughly evaluated to rule out any alternative etiology (e.g., disease progression, other medications, infections including testing for Clostridium difficile toxin, etc.) Steroids should be considered in the absence of clear alternative etiology, even for low grade events, in order to prevent potential progression to higher grade event 
Use analgesics carefully; they can mask symptoms of perforation and peritonitis

Grade 1	No dose modification	Actively monitor frequency, consistency and appearance of stools (especially for presence of mucus or blood) and for the emergence of abdominal pain or cramps
Grade 2	If on AL101 6 mg QW: For first episode, change dose regimen to 6 mg 2 weeks on / 1 week off Second episode, decrease dose to 4 mg QW and for third episode decrease dose to 2.4 mg QW If on AL101 4 mg QW: Decrease dose to 2.4 mg QW	
 Promptly start prednisone 1 to 2 mg/kg/day or IV equivalent Evaluate for C. difficile and, if positive, treat with appropriate antibiotics If event is not responsive within 3-5 days or worsens despite prednisone at 1-2 mg/kg/day or IV equivalent, GI consult should be obtained for consideration of further workup such as imaging and/or colonoscopy to confirm colitis and rule out perforation Consult Ayala Medical Monitor if no resolution to \leq Grade 1 in 3-4 days in order to determine whether to continue to hold the dose or to discontinue IP. This will depend on the overall clinical situation. Therapy may only be restarted with the dose reduction upon resolution to \leq Grade 1 
Once improving, gradually taper steroids over \geq28 days and consider prophylactic antibiotics, antifungals and anti PCP

Grade	Dose Modification	Management
		treatment (please refer to current NCCN guidelines for treatment of cancer-related infections [Category 2B recommendation])

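### Exclusion 6 misses Grade 2 or higher neuropathy that began less than 14 days before dosing, and Exclusions 4 and 5 disagree on residual Grade 1 immune-mediated colitis with no stated precedence

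*Combined protocol and SAP*

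**What the plan says.** Section 5.2 introduces its list with "The subjects must be excluded from participating in the study if they meet any of the following criteria", so one criterion met is enough to exclude. The preamble to Section 5 rules out waivers, and Section 8 repeats this.

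- **Exclusion 4** covers "Current or recent (within 2 months of IP administration) gastrointestinal (GI) disease or disorders that increase the risk of diarrhea". Its examples are inflammatory bowel disease and Crohn's disease. Immune-mediated colitis is not named. The only carve-out is for non-chronic conditions "that are completely resolved for at least 2 weeks prior to starting IP are not exclusionary".
- **Exclusion 5** excludes a subject who "Developed immune-mediated colitis with immunotherapy unless resolved to G1 or lower and without requirement of steroid treatment for at least 14 days" before the first dose.
- **Exclusion 6** excludes peripheral neuropathy at or above "Grade 2 for at least 14 days prior to first dose of IP".
- **Exclusion 8** lets the investigator exclude for an important illness "that would, in the investigator's judgment, increase the risk to the subject associated with his or her participation in the study". It sets no grade and no time limit.

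Nothing in Section 5.2 says whether Exclusion 5 replaces Exclusion 4 for immune-mediated colitis.

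**The concern.** In Exclusion 5 the 14-day period qualifies the absence of a need for steroids, so a longer period makes the rule more cautious. In Exclusion 6 the same period qualifies the presence of toxicity, which reverses its effect: the more recent the neuropathy, the less likely it is to be caught. A long-standing Grade 2 neuropathy is excluded while a Grade 3 neuropathy of a few days is not. The baseline grade matters later, because the general text of Section 6.4 lets dosing resume at Grade 1 or the baseline level, whichever is greater.

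For colitis, Exclusion 4 asks for complete resolution while Exclusion 5 tolerates Grade 1. Inclusion 4 allows prior immunotherapy, so such candidates are foreseeable. Section 8.3.5 makes colitis an adverse event of special interest and describes these events as having no clear alternate etiology. If sites differ on which criterion applies, the population differs by site in a feature that bears on how that event is attributed.

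**Working it through.** The plan gives no figure that depends on these criteria, so there is nothing numerical to reproduce. The check applies each rule literally to a set of cases and combines the results under the any-criterion rule.

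**Exclusion 6.** Literal rule: exclude if grade is 2 or higher and duration at first dose is 14 days or more.

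| Neuropathy at first dose | Lasting 1, 7 or 13 days | Lasting 14 or 30 days |
|---|---|---|
| Grade 1 | not excluded | not excluded |
| Grade 2 | not excluded | excluded |
| Grade 3 | not excluded | excluded |

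The gap is every Grade 2 or higher neuropathy that began less than 14 days before dosing. Other criteria in Section 5.2 use true look-backs: 2 months in Exclusion 4, and 7 days in Exclusions 7 and 17. Exclusion 6 departs from that form.

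**Exclusions 4 and 5.** Literal rules:

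- Exclusion 4 excludes if the condition is present, or was present within 2 months (taken as 60 days), unless it is non-chronic and has been fully cleared for at least 14 days.
- Exclusion 5 excludes unless the grade is 1 or lower and no steroids have been needed for at least 14 days.

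Assumptions: immune-mediated colitis counts as a GI disorder that raises diarrhea risk, and it is non-chronic.

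| Colitis at first dose | Days without steroids | Exclusion 4 | Exclusion 5 | Combined |
|---|---|---|---|---|
| Cleared 20 days ago | 7 | no | yes | excluded |
| Cleared 20 days ago | 14 or 30 | no | no | not excluded |
| Cleared 10 days ago | 7 | yes | yes | excluded |
| Cleared 10 days ago | 14 or 30 | yes | no | excluded |
| Grade 1 | 7 | yes | yes | excluded |
| Grade 1 | 14 or 30 | yes | no | excluded |
| Grade 2 | 7, 14 or 30 | yes | yes | excluded |

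Among the cases that Exclusion 5 would let through, the two criteria disagree in two: residual Grade 1 colitis, and colitis that cleared less than 14 days ago, each with at least 14 days without steroids. In both, the combined result is exclusion. The Grade 1 allowance in Exclusion 5 therefore never takes effect on this reading.

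**The case against.** **Exclusion 5 may be the specific rule.** Exclusion 4 does not name immune-mediated colitis and Exclusion 5 is devoted to it. Read as general rule and specific rule, they do not contradict each other. This is a reasonable reading, but the text does not state it. The examples in Exclusion 4 are illustrative, and Section 8.3.5.1 lists severe diarrhea among the signs of potential colitis, so it is hard to place colitis outside Exclusion 4.

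**A reader might infer that the conflict lets subjects with active colitis into the trial.** The documents do not support that. Exclusion 5 only declines to exclude; Exclusion 3, by contrast, says outright that certain subjects are eligible. If both criteria apply, the any-criterion rule excludes. What remains is inconsistent application across sites.

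**A reader might extend the point to the lead-in dose decision or to colitis management.** The documents give no usable rate for the first. The Grade 3 diarrhea count of 8/43 quoted in Section 4.3 comes from a study spanning 0.4 to 8.4 mg QW, is contrasted there with the rate under proactive diarrhea control, and lacks the lead-in rule's condition of more than 3 days' duration. For the second, Table 4 manages colitis during treatment and is not an eligibility rule.

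**Backstops exist for neuropathy.** Exclusion 8 can remove a subject on judgment, and Exclusion 10 (ECOG 2 or higher) removes those whose function is badly affected. Both are partial: neither refers to neuropathy grade, and the first depends on the investigator. It can also be said that Exclusion 6 was meant to catch only persistent neuropathy. If so, recent neuropathy of a worse grade is still left to judgment, and the intent should be stated. Neuropathy is not an adverse event of special interest for AL101 and does not enter the response endpoint, so the consequence is for subject safety and interpretation of adverse events, not for the primary analysis.

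**Conclusion.** The point holds in two parts of different strength.

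Exclusion 6 is defective as worded. Followed literally, it does not exclude Grade 2 or higher neuropathy of less than 14 days' duration. This rests only on the text.

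Exclusions 4 and 5 disagree for residual Grade 1 immune-mediated colitis, and for colitis cleared less than 14 days ago, when no steroids have been needed for at least 14 days. This rests on colitis falling under Exclusion 4, which is likely but not stated. Strictly applied, the list excludes these subjects, so enrollment with active toxicity follows from the wording for neuropathy only. For colitis the risk is that sites apply different rules.

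The size cannot be put in numbers: the documents do not say how many candidates have residual immune-mediated colitis or recent neuropathy. No sample size, error rate or power figure is affected. The corrections are cheap and bear on safety, so they should be made.

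**What to change.** 1. Reword Exclusion 6 so that the 14 days is no longer a minimum duration of the toxicity. State it either as a condition at entry or as a look-back period.
2. State which of Exclusions 4 and 5 governs immune-mediated colitis. Either Exclusion 4 says that this condition is handled by Exclusion 5 alone, or the resolution standard in Exclusion 5 is aligned with Exclusion 4. The chosen wording should also settle colitis that has cleared within the previous 14 days.

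The sponsor sets the grades and periods; none is proposed here.

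The cost is a few lines of amendment text in Section 5.2. No new assessment is needed, since Section 8.2.1 already has clinically significant history and abnormal screening findings recorded. The downside is that a few candidates change eligibility status.
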